- B) Premenopausal patients who have de-novo metastatic disease (metastatic disease at presentation).
- C) Premenopausal women who have not received Tamoxifen in the metastatic setting, but have received up to two lines of chemotherapy.

Post-Menopausal Women or Men

- D) Postmenopausal patients who have progressed on first-line or second-line therapy with an aromatase inhibitor in the metastatic setting
- E) Postmenopausal patients who have recurred while on or after completion of adjuvant treatment with aromatase inhibitors (they have completed at least one year of adjuvant AI in the adjuvant setting before progression on AI).
- F) Postmenopausal patients who are not considered candidates for treatment with an aromatase inhibitor by their oncologist , patients not willing not to go on to AI, or were intolerant to AI
- G) Post-menopausal women or men who have been treated with up to three lines in the escalation arm and up to two lines of chemotherapy in the dose expansion arm in the metastatic setting.

Type of Study

Open labeled, non-randomized; phase I dose escalation followed by phase Ib dose expansion

Prior Therapy

- Progression on any aromatase inhibitor for metastatic disease
- Recurrence ≥ 12 months after commencement of adjuvant aromatase inhibitors
- Patients are allowed (but not required) to have up to two prior chemotherapy regimens for metastatic disease

Rationale for Study

Cell cycle progression is directly regulated by cyclin-dependent serine-threonine protein kinases. The cyclin D proteins are important in cancer, as their abundance and functions are regulated by extracellular growth factor and adhesion signaling. The cyclin D proteins act through the CDK4 and CDK6 protein kinases to promote G1 progression (1). CDK4 and CDK6, in turn, hyperphosphorylate and activate the retinoblastoma protein Rb to promote cell cycle entry and cell proliferation. Consistent with their having an important role in human cancer, focal copy number abnormalities that result in increased CDK activity are among the most commonly described genetic events observed in diverse tumor types; these events

include amplifications of the genes that encode cyclin D1 or CDK4, and deletions affecting the CDKN2A locus, which encodes the p16INK4a inhibitor of CDK activity (2-4).

Data from The Cancer Genome Atlas highlight the importance of the Cyclin/CDK/Rb pathway in breast cancer (2, 3). Abnormalities that result in CDK activation are highly enriched in the luminal A and B molecularly defined subgroups, ~85% of which were ER+/Her2- (5). Cyclin D1 amplifications were observed in 29% and 58% of the luminal A and B subtypes, respectively, and CDK4 amplifications were observed in 14% and 25% of luminal A and B subtypes, respectively. Luminal A subtype tumors also have loss of CDKN2C, which encodes p16Ink4a, a CDK inhibitor. The luminal subtypes also maintain expression of Rb, which would be essential for benefit from treatment with a CDK4/6 inhibitor (2-4). PD0332991 is an oral, potent, selective inhibitor of CDK4/6 that was shown to inhibit proliferation and induce apoptosis in multiple preclinical models of endocrine-resistant breast cancer, both *in vitro* and *in vivo* (11, 4). In the clinic, PD0332991 was studied in a randomized Phase II study in combination with the non-steroidal aromatase inhibitor letrozole. This combination significantly prolonged median progression free survival in postmenopausal women with locally recurrent or advanced ER+/HER2+ breast cancer treated in the front-line setting (median PFS 26.1 vs 7.5 months, reported in Finn et al (6).

Most breast tumors that initially respond to anti-estrogen therapy acquire resistance in time. Given the above pre-clinical data, there may be benefit from a combination of Tamoxifen and Ribociclib, in women with hormone sensitive tumors as well as those whose tumors became unresponsive. Current and recently completed studies restrict CDK trials and limit the patient population to only postmenopausal patients but it is well known that younger, pre-menopausal and peri-menopausal patients often have more “aggressive” disease and more endocrine-resistant disease and this combination may be very helpful in delaying endocrine resistance in this patient population.

Rationale for the combination of CDK4/6 inhibitors with Tamoxifen plus goserelin

Multiple adjuvant studies have described amenorrhea as a positive prognostic factor in patients with overall survival after adjuvant chemotherapy. Based upon a number of adjuvant studies, the NCCN guidelines recommend goserelin to be strongly considered in premenopausal women who are menstruating despite receiving chemotherapy (7). In a retrospective study done at one hospital, over 150 patients with stage Ia to IIIa ER + breast cancer who received goserelin or chemotherapy were reviewed. Survival analysis was assessed by the Kaplan-Meier method. Survival at 11 years was significantly better in the goserelin group ($P < 0.0012$). The lifetime lost was lower in the goserelin group (42 months vs. 66 months). The quality adjusted survival (QAS) of patients who received goserelin was longer (122.5 ± 6.3 vs. 112.2 ± 6.7 months). The quality-adjusted life-year was higher in the goserelin group. Goserelin therapy results in better survival and higher utility-weighted life-years, and is more cost-effective (8). We plan to add goserelin to all women who are not postmenopausal. We estimate that of the 40 patients on study, approximately 20 will not meet the standard criteria of a post-menopausal state (no menstrual cycles for greater than 12 months and FSH of ≥ 40). We will not stratify for menopausal status. This

study is inclusive of all women regarding of menopausal status and explores the combination of Tamoxifen with this CDK4/6 inhibitor.

We will additionally explore two cohorts in the Phase Ib expansion. Having a continuous dosing cohort has multiple advantages. There is sustained inhibition of the cell cycle and less AEs. This cohort will allow us to further explore a cohort with increased safety and better patient compliance. Patients will not have to remember whether they are on the “on week” or the “off week.” Continuous dosing was done in Ph I CLEE011X2101 and both continuous and intermittent dosing revealed increased rates of grade 3 or 4 neutropenia rates at day 15 of every cycle on doses of 600 mg of Ribociclib and higher. **At lower doses, ribociclib had lower rates of neutropenia and continuous dosing should be tolerated.**

Type of Study:

Open labeled, non-randomized, Phase I escalation study with a Phase Ib dose expansion.

Phase I

The phase I portion of the study is a ***dose escalation*** to confirm the safety of the combination and to determine the MTD and the RP2D for ribociclib with Tamoxifen.

Phase I will be conducted in all patients with HR+/HER2- locally advanced or metastatic breast cancer with any prior endocrine therapy and up to three prior cytotoxic chemotherapy regimens administered in the metastatic or locally advanced setting.

Phase Ib dose expansion

Phase I trials are increasingly including dose-expansion cohorts (Ib) after the maximum-tolerated dose (MTD) has been reached to better characterize the toxicity profile and identify early signs of efficacy within this specific disease population. Our goal is to assess the anti-tumor activity Ribociclib + Tamoxifen and to further evaluate their safety in adult patients with HR+/HER2- locally advanced or metastatic breast cancer. Patients in the phase 1b expansion will have the same exclusion and inclusion criteria except that they will only be allowed to have up to two lines of cytotoxic chemotherapy in the metastatic setting.

Tamoxifen will be administered orally according to the standard regimen used in clinical practice (20 mg oral QD). Ribociclib will be administered orally, once daily for 21 consecutive days followed by a 7-day planned break (28-day cycle). In the *continuous dose cohort*, ribociclib will be administered daily (QD) without a break in each cycle. Tamoxifen will be administered in combination with ribociclib until disease progression or if unacceptable toxicity occurs that precludes any further treatment and/or if

treatment is discontinued at the discretion of the investigator or the patient, or the patient's death, whichever occurs first.

Phase I Study drugs (ribociclib dose may change depending on results of phase I)

TAMOXIFEN: 20 mg po daily

RIBOCICLIB: Phase I: starting at a dose of 400 mg po for 21 days of a 28-day treatment cycle; increased to 400 mg po daily (continuous dosing); increased to 600mg po daily for 21 days of a 28 day cycle.

Phase 1b expansion will look at two cohorts: 600 mg po for 21 days of a 28 day cycle with Tamoxifen and a continuous dosing cohort of ribociclib 400 mg daily with Tamoxifen.

Please note, that per NCCN guidelines for treatment of ER positive breast cancer, Goserelin acetate (Zoladex) (3.6 mg subcutaneous every 28 days) will be given per SOC practice to pre-menopausal and peri-menopausal women. This is standard of care for the treatment of pre- and peri- menopausal women and is not considered part of the study. The metabolism of goserelin is not CYP-mediated; rather hydrolysis of C-terminal amino acids is the major clearance mechanism. Based on the available information, goserelin is not expected to affect the metabolism of ribociclib nor be affected by co-administered drugs.

Safety Evaluation

Toxicity assessment, interim history and physical exam, CBC and chemistry profile weekly in cycle 1, then at day 1 of each cycle thereafter. Adverse Events and other symptoms will be assessed continuously and graded according to the NCI Common Toxicity Criteria, (CTCAE) v.4. Patients will be followed for evaluation of safety for at least 30 days after the last dose of study drug or until resolution of the AE. Any study drug-related serious adverse events will be followed until resolution, return to baseline grade, or deemed irreversible by the investigator.

Dose and Treatment Schedule

No of pts	Cohort Level	Ribociclib	Tamoxifen
3-6 (phase 1)	1	400 mg oral days 1-21, followed by 1 week break	20mg oral daily
3-6 (phase 1)	2	400 mg continuous	20 mg oral daily
3-6 (phase 1)	3	600 mg oral day 1-21 followed by 1 week break	20 mg oral daily

15 (dose expansion)	Phase Ib dose expansion	600 mg oral day 1-21 followed by 1 week break	20 mg oral daily
15 (dose expansion)	Phase Ib –dose continuous dosing cohort	400 mg oral daily	20 mg oral daily

* Goserelin acetate (Zoladex) 3.6 mg subcutaneous every 28 days will be given per NCCN guideline to pre-menopausal and peri-menopausal patients as described above. We will define this further in the full protocol.

* If the daily dosing is too bone marrow suppressive, then this arm will switch to 400 mg oral days 1-21, followed by 1 week break of a 28 day cycle.

Prohibited Medications:

- No other chemotherapy, hormonal therapy, radiotherapy, or experimental anticancer medications for the primary disease will be permitted while the patient is on study.
- Strong inhibitors or inducers of CYP3A4/5
- Substrates of CYP3A4/5 with narrow therapeutic windows
- Medications that carry a strong risk for QT prolongation
- Herbal medications/preparations not prescribed by treating MD

Statistical Considerations

Patient Population:

Patients with estrogen and/or progesterone receptor positive, HER2-negative advanced (metastatic) breast cancer that are in one of the following populations

Pre-menopausal Women:

- A. Pre-menopausal women who received adjuvant Aromatase Inhibitor and Ovarian Suppression (AI + OS) in the adjuvant setting and completed at least 12 months of hormonal therapy.
- B. Pre-menopausal women who have never been treated with endocrine therapy with de-novo metastatic disease.
- C. Pre-menopausal women who have not received Tamoxifen in the metastatic setting, but have received up to two lines of chemotherapy for dose expansion and up to three lines for dose escalation.

Post-Menopausal Women or Men

- D. Post-menopausal women or men who have progressed on first-line or second-line therapy with an aromatase inhibitor
- E. Post-menopausal women or men who have recurred while on or after completion of adjuvant treatment with aromatase inhibitors (they have completed at least one year of adjuvant AI in the adjuvant setting before progression on AI).
- F. Post-menopausal women or men who are not considered candidates for treatment with an aromatase inhibitor by their oncologist, refused AI, or intolerant to AI
- G. Post-menopausal women or men who have been treated with up to two lines of chemotherapy for dose expansion and up to three lines for dose escalation in the metastatic setting.

Total number of patients: 40

Number of Centers: 1 (will be adjusted, increased if accrual goals are not met).

Sample Size Justification (will be updated by statistician):

For a total of **40 subjects**, about 9-12 will be accrued during phase 1 portion and **about 30 patients for the phase 1b expansion.**

Part 1: phase 1 portion:

We will evaluate the first 9-12 patients in the phase I portion for safety.
The Primary objective is safety.

Part II: phase Ib expansion:

For the phase one expansion we will include pre- menopausal women, post-menopausal women, and men evaluated as one group. We will further evaluate both a three weeks on and one week off cohort (i.e. once daily for 21 consecutive days followed by a 7-day planned break) and a *continuous dose cohort* of ribociclib administered daily (QD) without a break in each cycle. Tamoxifen will be administered daily per standard of care in both cohorts.

The **primary objective** in the phase I study is to confirm safety, tolerability, confirm DLT, and determine the RP2D of Ribociclib with Tamoxifen

The **secondary objective** is to evaluate 2 dose expansion cohorts after the maximum-tolerated dose (MTD) has been reached to better characterize the toxicity profile and identify early signs of efficacy. Our goal is to assess the anti-tumor activity Ribociclib + Tamoxifen and to further evaluate their safety in adult patients with HR+/HER2- locally advanced or metastatic breast cancer.

To determine whether treatment with ribociclib improves response rate (RR) compared to the historical response rate with treatment with Tamoxifen alone. We know that the expected RR for Tamoxifen after failure of first line AI is about 10 % and therefore we hypothesize an improvement of RR to 25%.

Efficacy Evaluation

Response and progression will be evaluated in this study using the new international criteria proposed by the Response Evaluation Criteria in Solid Tumors (RECIST 1.1). This will be expanded in protocol.

DEFINITIONS:

DLT – Dose-Limiting Toxicity

MTD – Maximum tolerated dose

PFS – Progression-Free Survival

DDI – Drug-Drug Interaction

ER – Estrogen Receptor

PR – Progesterone Receptor

HER2 – Human Epithelial Receptor 2

PO – by mouth (per orum)

SERMS (selective estrogen receptor modulators)

SOC – standard of care

RR- Response Rate

FIH – First in human

Protocol:

The TEEL Study: A Phase I trial of Tamoxifen with Ribociclib (LEE011) in adult patients with advanced ER+ (HER2 negative) breast cancer.

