 - b. Female sterilization (have had surgical bilateral oophorectomy with or without hysterectomy) or tubal ligation at least six weeks before taking study treatment. In case of tubal ligation alone, only when the reproductive status of the woman has been confirmed by follow up hormone level assessment.
 - c. Male sterilization (at least 6 months prior to screening). For female patients on the study, the vasectomized male partner should be the sole partner for that patient
 - d. No patients with HR+ disease should receive hormonal contraception, however the two following methods can be combined: Placement of an intrauterine device (IUD) or intrauterine system (IUS and barrier methods of contraception: Condom or Occlusive cap (diaphragm or cervical/vault caps) with spermicidal foam/gel/film/cream/ vaginal suppository.

Note: The use of oral contraception is not allowed.

Women are considered **post-menopausal** and not of child bearing potential if they have had 12 months of natural (spontaneous) amenorrhea with an appropriate clinical profile (e.g. age appropriate, history of vasomotor symptoms) or have had surgical bilateral oophorectomy (with or without hysterectomy) or tubal ligation at least six weeks ago. In the case of oophorectomy alone, only when the reproductive status of the woman has been confirmed by follow up hormone level assessment is she considered not of child bearing potential.]

- Patients who meet the eligibility criteria may be registered and enrolled on the trial. We will complete phase I portion of the study before proceeding to phase Ib expansion. At time of phase Ib expansion, we will alternate enrollment to both cohorts of our study, until both cohorts are complete.
- A signed copy of the institution's IRB-approved informed consent document must be placed on file.
- Patients must not start protocol treatment prior to registration.

7 TREATMENT PLAN:

Investigational Study Treatment

RIBOCICLIB will be supplied by Novartis or its designee in the form of 200 mg hard gelatin capsules/tablets as individual patient supply packaged in bottles.

All dosages prescribed and dispensed to the patient and all dose changes during the study must be recorded.

Dose and treatment schedule

Study treatment	Pharmaceutical form and route of administration	Dose	Frequency and/or Regimen
RIBOCICLIB	Capsules/tablets for oral use	400 mg	21 days on and 7 days off Or Daily (in continuous cohort)

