7.1 Dose Modifications

Dose Limiting toxicity (DLT) is defined as an adverse event or abnormal laboratory value assessed as having a reasonable possibility of relatedness to the study medication, unrelated to disease, disease progression, inter-current illness, or concomitant medications that occurs within the first 28 days of treatment (cycle 1) with RIBOCICLIB and Tamoxifen and meets any of the criteria included in below [modification tables](#). National Cancer Institute Common Terminology Criteria for Adverse events (NCI CTCAE) **version 4.03** will be used for all grading.

In this study, a DLT will occur if CTCAE grade 4 neutropenia lasts more than 4 consecutive days, if CTCAE grade 3 thrombocytopenia is associated with clinically significant bleeding or if there is grade 4 thrombocytopenia. Please see the following table (7-1) for other DLT criteria.

Table 7-1 Criteria for defining dose-limiting toxicities

TOXICITY	DLT CRITERIA
Hematology	≥ CTCAE grade 4 neutropenia lasting more than 4 consecutive days
	CTCAE grade 3 thrombocytopenia with clinically significant bleeding
	CTCAE grade 4 thrombocytopenia
	Febrile neutropenia (decrease in neutrophils associated with fever, ANC <1.0 x 10 ⁹ /L, fever ≥38.5°C)
	CTCAE grade 4 lymphopenia lasting more than 7 consecutive days
Skin and subcutaneous tissue disorders	CTCAE grade 3 Rash > 7 days despite optimal management and does not resolve to Grade 0 or 1
	CTCAE grade 4 Rash that is thought to be related to study drug
	≥ CTCAE grade 3 photosensitivity
Metabolism	Grade 2 hyperglycemia (Fasting glucose 200 – 249 mg/dL) (confirmed with a repeat Fasting glucose within 24 hours) that does not resolve to Fasting glucose <200 mg/dL within 14 consecutive days (despite optimal oral anti-diabetic therapy, i.e. glimepiride, glibenclamide and/or metformin)
	Grade 3 hyperglycemia (Fasting glucose 250-499 mg/dL) (confirmed with a repeat Fasting glucose within 24 hours) for > 14 consecutive days despite optimal oral anti-diabetic treatment
	Grade 4 hyperglycemia (Fasting glucose >499 mg/dL)
	Hyperglycemia leading to diabetic keto-acidosis, hospitalization for IV insulin infusion, or non-ketotic coma
	CTCAE grade 3 amylase and/or lipase, not reversible to ≤ CTCAE grade 2 for > 7 consecutive days
Gastro-intestinal	CTCAE grade 4 amylase and/or lipase
	≥ CTCAE grade 3 vomiting ≥ 48 hrs despite optimal anti-emetic therapy
	≥ CTCAE grade 3 diarrhea ≥ 48 hrs despite optimal anti-diarrhea treatment

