Grade 3 ($0.5 - <1.0 \times 10^9/L$)	Dose interruption until recovery to $>1.0 \times 10^9/L$. Re-initiate ribociclib at the same dose level. • If toxicity recurs at grade 3: temporary dose interruption until recovery to $>1.0 \times 10^9/L$. If resolved in ≤ 7 days, then maintain dose level. If resolved in > 7 days, reduce ribociclib dose to the next lower dose level.
Grade 4 ($<0.5 \times 10^9/L$)	Dose interruption until recovery to $\geq 1.0 \times 10^9/L$. Re-initiate ribociclib at the next lower dose level. • If toxicity recurs at grade 4: temporary dose interruption until recovery to $\geq 1.0 \times 10^9/L$ and reduce ribociclib at the next lower dose level.
Febrile neutropenia	
Grade 3 ANC $<1.0 \times 10^9/L$ with a single temperature of $>38.3^\circ C$ ($101^\circ F$) or a sustained temperature of $\geq 38^\circ C$ ($100.4^\circ F$) for more than one hour	Dose interruption until improvement of ANC $\geq 1.0 \times 10^9/L$ and no fever. Restart at the next lower dose level. • If febrile neutropenia recurs, discontinue ribociclib.
Grade 4 Life-threatening consequences; urgent intervention indicated	Discontinue ribociclib.
Anemia (Hemoglobin)	
Grade 1 ($\geq 10.0 - LLN$ g/dL)	No dose adjustment required.
Grade 2 ($\geq 8.0 - 10.0$ g/dL)	No dose adjustment required.
Grade 3 (<8.0 g/dL)	Dose interruption until recovery to grade ≤ 2 . Re-initiate RIBOCICLIB at the same dose.
Grade 4 Life-threatening consequences; urgent intervention indicated	Discontinue ribociclib.

Table 7-4 Recommendations for ribociclib dose modification in case of hepatic toxicities

HEPATOTOXICITY (BILIRUBIN, SGPT/ALT, SGOT/AST)
TOTAL BILIRUBIN without ALT/AST increase above baseline value

Grade 1 ($>$ ULN – 1.5 x ULN) (confirmed 48-to 72hrs later)	Maintain dose level with LFTs monitored bi-weekly
Grade 2 ($>$ 1.5 – 3.0 x ULN)	Dose interruption of ribociclib If resolved to \leq grade 1 in \leq 21 days, then maintain dose level If resolved to \leq grade 1 in $>$ 21 days or toxicity recurs, then reduce 1 dose level If toxicity recurs after two dose reductions, discontinue ribociclib
Grade 3 ($>$ 3.0 – 10.0 x ULN)	Dose interruption of ribociclib If resolved to \leq grade 1 in \leq 21 days, lower 1 dose level of ribociclib If resolved to \leq grade 1 in $>$ 21 days or toxicity recurs, discontinue ribociclib
Grade 4 ($>$ 10.0 x ULN)	Discontinue ribociclib

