8 TREATMENT PLAN

Phase I/ Phase Ib dose expansion:

TAMOXIFEN: 20 mg PO daily will be given with RIBOCICLIB:

Ribociclib (LEE011)

In phase I: Ribociclib PO starting at a dose of 400 mg po for 21 days of a 28-day treatment cycle; this will be increased to 400 mg continuously. We will then evaluate 600 mg po daily for 21 days of a 28 day cycle if tolerated.

If there are no dose limiting toxicities, in the phase I portion, Tamoxifen 20 mg will be given with the MTD dose of Ribociclib in 15 patients. This is expected to be 600mg three weeks on and one week off. These patients will *not be stratified* for menopausal status.

If the 400mg continuous dose was well tolerated in the escalation arm, we will then expand this cohort in the phase Ib expansion, we will have an additional cohort of Tamoxifen 20 mg with 400 mg ribociclib in a continuous daily dose in an additional 15 patients. These patients will *not be stratified* for menopausal status.

Goserelin acetate (Zoladex) (3.6 mg subcutaneous every 28 days) will be given per NCCN guidelines to pre-menopausal and peri-menopausal. This will be given on day 1 of every cycle. We estimate that up to 20 of 40 patients on this protocol will require goserelin.

Goserelin is given if patient is premenopausal or peri-menopausal at the time of study entry.

Premenopausal status is defined as either:

- Patient had last menstrual period within the last 12 months.
- In case of therapy induced amenorrhea, with a plasma estradiol ≥ 10 pg/mL and/or FSH ≤ 40 IU/l or in the premenopausal range according to central laboratory definition.
- Patients who have undergone bilateral oophorectomy do not need goserelin.

Peri-menopausal status is defined as neither premenopausal nor postmenopausal (see exclusion criteria for definition).

8.1 Study Design:

Dose and Treatment Schedule – Table 8-1

No of pts	Cohort Level	RIBOCICLIB	Tamoxifen
3-6 (phase 1)	1	400 mg oral days 1-21, followed by 1 week break	20mg oral daily
3 -6 (phase 1)	2	400mg continuous	20 mg oral daily
3 -6 (phase 1)	3	600 mg oral day 1-21 followed by 1 week break	20 mg oral daily
15 (Ib dose expansion)	Phase Ib dose expansion	600 mg oral day 1-21 followed by 1 week break	20mg oral daily
15 (Ib dose	Phase Ib dose expansion-	400 mg oral daily	20 mg oral daily

expansion	continuous cohort	
------------------	--------------------------	--

Ribociclib Capsules/tablets for oral use 400 mg OR 600 mg Days 1-21 of each 28 day cycle or daily.

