10 STATISTICAL CONSIDERATIONS

10.1 Statistical Considerations for Phase I Study

A standard 3+3 design will be used (33) for the primary toxicity study under Phase I. A cohort of 3 patients will be recruited for each dose level at a time at a time. The first dose level will be level 1 and gradually increased to Level 2 and 3 if toxicity AEs are observed within the predefine statistical criterion/limit below.

Level 1: Ribociclib PO starting at a dose of 400 mg po for 21 days, followed by 1 week break of a 28-day treatment cycle;

Level 2: Ribociclib PO treated with a dose of 400 mg po daily for 28 days;

Level 3: Ribociclib PO treated with a dose of 600 mg po for 21 days, followed by 1 week break of a 28-day treatment cycle

If 1 patient out of 3 experiences a dose limiting toxicity (DLT; see below for definition) at level 1, 3 additional patients will be recruited at that dose level. If only 1 out of 6 patients in that dose level experiences a DLT, a new cohort of 3 patients will be treated with the next escalated dose level. That is, the dose escalation continues until at least two patients among a cohort of three to six patients experience dose-limiting toxicities (i.e., $\geq 33\%$ of patients with a dose-limiting toxicity at that dose level). If 2 out of 3 or 2 out of 6 patients experience a DLT, no further dose escalation will occur. The recommended phase II dose (RP2D) is defined as the dose level at which $\leq 1/6$ patients experience DLT. There will be no dose escalation beyond dose level 3, meaning that if $\leq 1/6$ patients experience DLT at this level, dose level will become the RP2D. No intra-patient dose escalation is allowed. Our dose escalation schedule follows a modified Fibonacci sequence in which the dose increments become smaller as the dose increases (e.g., the

dose first increases by 100% of the preceding dose, and thereafter by 50%, 33%, and 25% of the preceding doses). The RP2D will be defined as the dose level just below this toxic dose level.

Patients who achieve complete response (CR) or partial response (PR) or have stable disease (SD) may continue on study treatment until disease progression, as defined by RECIST v1.1 criteria, or intolerable toxicity.

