10.2 Statistical Considerations for Phase Ib Dose expansion Study

If no MTD is observed with Level 1 through 3, we plan to continue/conduct the phase Ib dose expansion study as below. This expansion study is planned to understand and obtain initial efficacy data for the secondary endpoints.

Since the identical patient inclusion/exclusion criteria will be used in phase Ib dose expansion, all patient data from phase I dose escalation and phase Ib dose expansion studies can be combined for our statistical analysis, therefore, the required sample size of patients below will be both for phase I dose escalation and phase Ib dose expansion studies.

We obtained our statistical power and required sample size as a single-arm prospective study. In particular, for our evaluation of early efficacy we designed the study particular, for our evaluation of early efficacy we designed the study for testing $H_0: P \leq 0.10$ versus $H_1: P \geq 0.25$ at one-sided significance level 0.05 and power 0.80 as below.

P0	P1	Alpha	Beta	Cut-Off		Actual	Actual
				R + 1	N		
0.100	0.250	0.050	0.200	8	40	0.042	0.182

Where P0 is the maximum response proportion of standard care (tamoxifen alone), P1 is the minimum response proportion of our experimental treatment group, and N is the sample size.

For our statistical testing, if the number of responses $\geq R+1$, P0 is rejected based on Fisher's Exact test (34, 35). Alpha is the probability of rejecting that $P \leq P_0$ when this is true.

Beta is the probability of rejecting that $P \geq P_1$ when this is true.

Thus, the study requires 6 subjects under phase I dose escalation and 30 subjects under phase Ib dose expansion who will be treated with ribociclib (total 36) in order to test whether the proportion responding, P, is less than or equal to 0.100 or greater than or equal to 0.25. If the number of responses is 8 or more, the hypothesis that $P \leq 0.100$ is rejected with a target Type I error rate, α , of 0.050 and an actual error rate of 0.045. The null hypothesis will be rejected if 8 or more responses are observed in 40 patients. This design yields a type I error rate of 0.045 and power of 0.818 when the true response rate is 0.25.

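### In the visible text, no DLT count triggers a review once Phase Ib opens and its two cohorts of 15 are filling; a pause-for-review rule would be a cheap addition with modest expected benefit

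*Combined protocol and SAP*

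**What the plan says.** All references are to the combined protocol and SAP.

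- **Before expansion.** Section 10.1 sets a 3+3 for Phase I: "That is, the dose escalation continues until at least two patients among a cohort of three to six patients experience dose-limiting toxicities". A DLT is an event "that occurs within the first 28 days of treatment (cycle 1) with RIBOCICLIB and Tamoxifen" (section 7.1).
- **Entry to expansion.** Section 10.2 says "If no MTD is observed with Level 1 through 3, we plan to continue/conduct the phase Ib dose expansion study as below". Section 8 gives the continuous cohort its own condition: "If the 400mg continuous dose was well tolerated in the escalation arm, we will then expand this cohort in the phase Ib expansion".
- **During expansion.** Table 8-1 gives two cohorts of 15. The registration bullets after the exclusion criteria say "we will alternate enrollment to both cohorts of our study, until both cohorts are complete". The only numerical decision rule in section 10.2 concerns response. Section 10.3, on safety statistics, gives an assessment schedule and follow-up but no count. Section 3.1 lists further safety evaluation in Phase Ib under the primary objective.
- **Other safeguards.** Sections 7.1 and 7.2 act patient by patient; for recurrent grade 3 neutropenia that is slow to resolve, for instance, Table 7-3 says "reduce ribociclib dose to the next lower dose level". Sections 13.2 and 13.3 allow suspension or termination of the study on qualitative grounds.
- **Synopsis footnote to the dose table.** "If the daily dosing is too bone marrow suppressive, then this arm will switch to 400 mg oral days 1-21", followed by the week's break. It is not repeated under Table 8-1.

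**The concern.** Escalation treats 3 to 6 patients per level, so most cycle 1 toxicity evidence on each expansion regimen will come from its 15 expansion patients. A regimen can pass the 3+3 by chance with a DLT rate that nobody would accept. If that happens, no stated number of DLTs brings the accumulating data to anyone for a decision. The per-patient rules protect someone who has already had an event; they do not hold back the next enrolment. The study-level clauses depend on someone choosing to use them, and an expected toxicity occurring too often might not prompt that.

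At stake is how many patients start a regimen whose toxicity is already visible in the cohort.

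**Working it through.** **Plan's own figure.** No Phase Ib safety figure is stated. The one design figure covering expansion is the response rule (40 patients, cut-off 8). Exact binomial gives alpha 0.0419 and power 0.8180, matching the table's 0.042 and 0.818 (1 minus 0.182). It says nothing about toxicity.

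**Inputs.** From the plan: 3+3 counts (10.1), 28-day DLT window (7.1), 15 per cohort (8.1). Assumed: the true DLT rate p, for which the plan gives no value. Rates of 33%, 40% and 50% stand for too toxic, and 15%, 20% and 25% for acceptable.

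**Step 1: passing the 3+3 at one level.** A level passes with 0 of 3, or with 1 of 3 then 0 of 3:

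P(pass) = (1-p)^3 + 3p(1-p)^5

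- p = 0.33: 0.30076 + 0.13366 = 0.434
- p = 0.40: 0.21600 + 0.09331 = 0.309
- p = 0.50: 0.12500 + 0.04688 = 0.172

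**Step 2: what 15 patients would show with no rule.** Expected DLTs are 15p, about 5, 6 and 7.5. The chance of 5 or more is 0.59, 0.78 and 0.94.

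**Step 3: an example boundary.** Take the smallest x with P(rate > 0.33 | Beta(0.33 + x, 0.67 + n - x)) > 0.80, using expansion patients only. For n = 4 to 15 this gives x = 3, 3, 4, 4, 4, 5, 5, 6, 6, 6, 7, 7. At n = 3 the formula would allow a pause at 2 of 3. I do not use that look, because it raises the pause probability at 15%, 20% and 25% to 0.08, 0.15 and 0.24. A 3 of 3 pause is allowed. It changes no pause probability, since a cohort with 3 of 3 has at least 3 of 4 at the next look.

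**Step 4: pause probability, by exact recursion over patients.**

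| True DLT rate | Pause, given entry | Pass 3+3 at that level | Product |
|---|---|---|---|
| 33% | 0.379 | 0.434 | 0.16 |
| 40% | 0.576 | 0.309 | 0.18 |
| 50% | 0.815 | 0.172 | 0.14 |

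At acceptable rates of 15%, 20% and 25%, the pause probability given entry is 0.040, 0.096 and 0.183. For at least one of two independent cohorts, 1 - (1 - q)^2 gives 0.08, 0.18 and 0.33.

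**Step 5: patients spared.** With looks from the fourth patient, mean enrolment at 33%, 40% and 50% is 11.92, 10.29 and 7.98 of 15 if each outcome is known before the next entry. It is 12.99, 11.92 and 10.32 if three more patients enter while outcomes are pending. Multiplying the shortfall from 15 by P(pass) gives:

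- immediate outcomes: 0.434 × 3.08 = 1.3; 0.309 × 4.71 = 1.5; 0.172 × 7.02 = 1.2 patients
- three pending: 0.434 × 2.01 = 0.9; 0.309 × 3.08 = 1.0; 0.172 × 4.68 = 0.8 patients

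**Step 6: sensitivity to borrowing.** Counting 0 of 3 from escalation at the same 0.80 cutoff moves the limits to 4 of 4-5, 5 of 6-7, 6 of 8-10, 7 of 11-12 and 8 of 13-15. The pause probability then falls to 0.285 at 40% and 0.570 at 50%.

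**The case against.** **The expected gain is small.** This stands. The 3+3 already makes entry of a too-toxic regimen uncommon, and about one patient per cohort is spared on average. Against that, an acceptable regimen is sometimes paused. A like-for-like comparison should weight both sides by entry. At 20% and 25% the 3+3 passes with probability 0.709 and 0.600, so an unnecessary pause has overall probability 0.709 × 0.096 = 0.07 and 0.600 × 0.183 = 0.11 per cohort, against 0.14 to 0.18 for a useful one.

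**Expansion patients are already protected.** A reader might infer that they have no safety net. The documents do not support that. There are interruption, reduction and discontinuation rules, weekly cycle 1 assessments, 24-hour reporting of serious events, and powers to suspend or terminate. What is missing is narrower: a count that obliges someone to look at a cohort.

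**The footnote may not be a Phase Ib trigger.** A reader might infer that Phase Ib rests on a switch with no event, count or timing. That is one reading only. The regimen switched to is dose level 1, the same table lists level 2 as continuous 400 mg, and section 8 makes the continuous cohort depend on tolerability in escalation. If the footnote means level 2, section 10.1 supplies the count and section 7.1 the window and the event; for marrow, for example, "a DLT will occur if CTCAE grade 4 neutropenia lasts more than 4 consecutive days". The footnote cites neither section, so the reading is open.

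**Entry to the continuous cohort might seem tighter still.** A reader of section 10.2 alone might require levels 2 and 3 both to pass and derive a much lower entry probability. Section 8 gates that cohort separately, and section 3.1 describes expansion after the MTD is reached, so no such bound is established. I use the single-level figures.

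**A procedure could sit in text not seen.** The Internal Monitoring heading in section 13 shows no text of its own before 13.1, and other text is redacted. The point is therefore limited to the visible text.

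**Conclusion.** The point holds as a gap in the visible plan: the DLT count ends with Phase I, while Phase Ib, which has safety among its primary aims, fills 30 places without one. It contradicts no figure in the plan, and it does not show that expansion is unsafe.

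The benefit is modest: an overall chance of about 0.14 to 0.18 of a useful pause per cohort at true rates of 33% to 50%, and roughly one patient spared. These figures rest on the assumed DLT rates and on my choice of prior, cutoff and non-borrowing. They also assume that outcomes are counted in order of entry. Under the fix a DLT counts on the day it occurs and a clean patient only at day 28, so early counts can run ahead and pauses of both kinds may be somewhat more frequent than shown. The gap itself does not depend on this particular boundary.

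Rating: optional to recommended. The footnote is a clarification and would not merit a point alone.

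**What to change.** Add to section 10.2: enrolment to an expansion cohort pauses for Protocol Monitoring Committee review when cycle 1 DLTs, among its expansion patients who have either had a DLT or completed the 28-day window, reach 3 of 3-5, 4 of 6-8, 5 of 9-10, 6 of 11-13 or 7 of 14-15. That denominator matters: counting only completed windows would delay an early DLT, or lose it if the patient withdraws. State that escalation patients are left out on purpose, because they were selected by passing the 3+3. The sponsor may substitute another prior, cutoff or borrowing rule and should then report its pause probabilities.

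For the footnote, one line suffices. If it refers to escalation level 2, cite section 10.1; if to the expansion cohort, tie it to the same pause rule.

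The cost is a paragraph and a small table. No new data are needed, since cycle 1 toxicity is already assessed weekly. The downside is an unnecessary pause at the rates given above, and a pause leads to review, not closure.
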